1	0	Predose ^d	00:00	X		X a,b,c	Predose PK samples will be collected from all study subjects to assess branebrutinib and relevant concomitant medications; For subjects on HCQ, whole blood samples will be collected for HCQ level assessment.
1	0	Postdose ^e	00:30	X	X		Postdose PK samples collected from all study subjects at these time points will be assessed for branebrutinib;
1	0	Postdose	01:00	X	X		Postdose PK samples collected at these time points from subjects
1	0	Postdose	02:00	X	X	X a,b,c	at preselected clinical sites will also be assessed for metabolites;
1	0	Postdose	04:00	X	X		Postdose PK samples collected at 2 hours after dosing will be assessed for relevant concomitant medications; For subjects on HCQ, whole blood samples will be collected for HCQ level assessment.
1	0	Postdose	06:00	X	X		Postdose PK samples collected from subjects at preselected
1	0	Postdose	08:00-10:00	X	X		clinical sites only will be assessed for branebrutinib and metabolites at these time points.
1	0	Postdose	10:00-12:00	X	X		· ·
2	0	Postdose ^f	24:00	X	X		
29	4	Predose	00:00	X		X a,b,c	Predose PK samples will be collected from all study subjects for assessment of branebrutinib and concomitant medications; For subjects on HCQ, whole blood samples will be collected for HCQ level assessment.
29	4	Postdose	02:00			X a,b,c	Plasma samples will be collected from all study subjects at 2 hours after dosing for assessment of relevant concomitant medications; For subjects on HCQ, whole blood samples will be collected in addition for HCQ level assessment.

Protocol Amendment No.: 04

Date: 01-Dec-2021

SLE Table 8 PK Sampling Schedule for Branebrutinib, Metabolites, and Concomitant Medications

Study Day	Study Week	Event	Time (Relative to Branebrutinib Dose) Hours:Minutes	Branebrutinib	Metabolites (collected from subjects at preselected sites only)	Concom Meds ^{a,b,c}	Comments
57	8	Predose	00:00	X	X		Predose and postdose PK samples collected from all study
57	8	Postdose	00:30	X	X		subjects will be assessed at these time points for branebrutinib only;
57	8	Postdose	01:00	X	X		• Predose and postdose PK samples collected at these time points from subjects at preselected clinical sites will also be assessed for
57	8	Postdose	02:00	X	X		metabolites.
57	8	Postdose	04:00	X	X		
57	8	Postdose	06:00	X	X		Postdose PK samples collected from subjects at preselected
57	8	Postdose	08:00-10:00	X	X		clinical sites only will be assessed for branebrutinib and metabolites at these time points.
57	8	Postdose	10:00-12:00	X	X		an alos tant points.
113	16	Predose	00:00	X			• Predose PK samples taken from all study subjects will be assessed for branebrutinib only.
169	24	Predose	00:00	X			• Predose PK samples taken from all study subjects will be assessed for branebrutinib only.
169	24	Postdose	00:30	X			Postdose PK Samples taken from all study subjects will be
169	24	Postdose	01:00	X			assessed at these time points for branebrutinib only.
169	24	Postdose	02:00	X			
169	24	Postdose	04:00	X			

PK = pharmacokinetic; Concom Meds = concomitant medications; HCQ = hydroxychloroquine.

Protocol Amendment No.: 04

Date: 01-Dec-2021

Approved v2.0 930168072 2.0

^a Concentrations of Concomitant medications that are sensitive substrates of CYP2C8 and other potentially relevant drug metabolizing enzymes that may have a drug-drug interaction with branebrutinib and P-gp transporter may be evaluated post-hoc for subjects receiving PBO and active treatment at predose of branebrutinib on Day 1 and Day 29 (see Section SLE 8.5.1).

b For subjects taking HCQ on-study, whole blood samples will be taken at predose and 2 hours after dosing with the IP on Day 1 (Week 0) and Day 29 (Week 4) (see Section SLE 8.5.1).

- Subjects who are on HCQ will be informed to bring HCQ to the clinic on Day 1 and Day 29 for simultaneous dosing with branebrutinib and not to take it at home on those 2 days. Similarly, subjects who are on other prescription concomitant medications will also be informed to bring them to the clinic on Day 1 and Day 29 for simultaneous dosing with branebrutinib, but only when it is safe for subjects and operationally feasible. This should be based on the investigator's discretion with consideration that the medications which should not be delayed until the time of dosing in the clinic should be taken at home. The self-reported time for all prescription medications taken at home should be recorded as accurately as possible.
- d Predose sample to be drawn within 1 hour before dose administration.
- ^e Postdose sample to be drawn within ± 15 min of the given time points.
- f PK sample must be drawn before the IP dose is administered on Day 2.

Protocol Amendment No.: 04

Date: 01-Dec-2021

SLE 8.5.1 PK of Potential Concomitant Medications

[figure not shown]
Concentrations of concomitant medications that are sensitive substrates of CYP2C8 and other potentially relevant drug metabolizing enzymes and P-gp transporter may be evaluated for subjects receiving PBO and active treatment with the bioanalytical analysis as part of a retrospective analysis. HCQ will be among the concomitant medications. The retrospective analysis will be conducted after review of the enrollment records, reported concomitant medication use within the enrolled population and on the incidence threshold and relevance to drug interaction with branebrutinib based on preclinical and clinical data. Other confounding factors will be evaluated as part of the analysis to avoid inclusion of bias or artifact results. Subjects who are on HCQ will be informed to bring HCO to the clinic on Day 1 and Day 29 for simultaneous dosing with branebrutinib and not to take it at home on those 2 days. Similarly, subjects who are on other prescription concomitant medications will also be informed to bring them to the clinic on Day 1 and Day 29 for simultaneous dosing with branebrutinib, but only when it is safe for subjects and operationally feasible. This should be based on the investigator's discretion with consideration that the medications which should not be delayed until the time of dosing in the clinic should be taken at home. The self-reported time for all prescription medications taken at home should be recorded as accurately as possible.

Concentrations of the relevant concomitant medications will be measured post-hoc using samples collected predose of branebrutinib or placebo on both Day 1 and Day 29 (Week 4; at which point accumulation of branebrutinib and its metabolites is expected to achieve steady-state). In addition to predose samples on Day 1 and Day 29, samples will also be collected at 2 hours after dosing with branebrutinib or placebo to evaluate the concentration of relevant concomitant medications, including HCQ. Bioanalytical analysis of all relevant concomitant medications will be conducted post-hoc. The doses of the concomitant drugs and the time they are taken, will be carefully recorded at all times (including Day 1 on Week 0 and on Day 29 on Week 4). Actual and dose-normalized concentrations will be listed, summarized, and compared between posttreatment and pretreatment of branebrutinib and PBO separately; other covariates such as MTX use, gender, etc. can be added to the comparison as needed.

[figure not shown]
Detailed instructions for PK sample collection for the relevant concomitant medications, labeling, processing, storage, shipping, and disposition are provided in the Laboratory Manual. While blood samples will be used for the analysis of HCQ, plasma samples will be analyzed for the other relevant concomitant medications by available validated assays. The results of these post hoc analyses will not be recorded in the clinical study report (CSR).

[figure not shown]
Protocol Amendment No.: 04

Date: 01-Dec-2021

SLE 8.7 Health Economics OR Medical Resource Utilization and Health Economics

Health Economics/Medical Resource Utilization and Health Economics parameters will not be evaluated in this study.

SLE 9 STATISTICAL CONSIDERATIONS

SLE 9.1 Sample Size Determination

Sample size is calculated based on the estimated effect size for the primary endpoint comparison between branebrutinib and PBO treatment groups. The primary endpoint for the SLE sub-protocol is $\geq 50\%$ decrease from baseline mCLASI activity score in subjects with a baseline mCLASI activity score ≥ 10 , at Week 24 and CS (prednisone or equivalent) ≤ 10 mg/day at Week 20 and Week 24.

Estimates for PBO response rates, treatment differences, and common standard deviations were obtained from the published literature. ⁷⁵

Assuming a total sample size of 60 subjects randomized in a blinded fashion in a 3:1 ratio to branebrutinib (45 subjects) or PBO (15 subjects) and a treatment difference of 25% with a PBO response of 30% for mCLASI at Week 24, the 95% CI is expected to exclude 0 (expected 95% CI based on a z-test = 2%, 56%).

Clinical Protocol BMS-986195

SLE 9.2 Populations for Analyses

For purposes of analysis, the following populations are defined:

Population	Description
Enrolled Set	All subjects who sign informed consent.
Full Analysis Set (FAS)	All subjects who were randomized. Following the intent-to-treat principle, subjects will be analyzed according to the treatment assigned at randomization. The FAS will be the primary efficacy analysis population. This is the same as the intent-to-treat population.
Per Protocol Set (PPS):	A subset of the FAS who are compliant with study treatment and who do not have any statistically relevant protocol deviations that may impact the primary efficacy endpoint assessments. The PPS will be analyzed according to the treatment assigned at randomization. The PPS may be a supportive efficacy analysis population.
Safety Analysis Set	All randomized subjects who receive at least 1 dose of double-blind study treatment. Subjects will be analyzed according to treatment received.
PK	All randomized subjects who receive at least 1 dose of branebrutinib and have any available branebrutinib concentration data. Subjects will be analyzed according to the treatment received during the PK collection.
Biomarker	All randomized subjects who receive at least 1 dose of double-blind study treatment and have at least 1 posttreatment biomarker measurement.

SLE 9.3 Endpoints

The following sections outline the efficacy endpoints for the SLE sub-protocol.

SLE 9.3.1 Primary Endpoint

Proportion of subjects with

• ≥ 50% decrease from baseline mCLASI activity score in subjects with a baseline mCLASI activity score ≥ 10, at Week 24

AND

• CS (prednisone or equivalent) ≤ 10 mg/day at Week 20 and Week 24

SLE 9.3.2 Secondary Endpoints

The following are the secondary efficacy endpoints as defined at Week 24:

- Change from baseline in SLEDAI-2K score
- BICLA response

Protocol Amendment No.: 04

Date: 01-Dec-2021

SLE 9.3.3 Additional Endpoints

The following are the additional efficacy endpoints as defined at Week 24:

- Change from baseline in:
 - Autoantibody titers (ANA, anti-dsDNA)
 - o Complement (C3, C4)
 - High-sensitivity C-reactive protein (hsCRP)
 - o Erythrocyte sedimentation rate (ESR)
 - o SGA of Disease Activity
 - o PGA of Disease Activity
 - Tender joint counts (TJC), swollen joint counts (SJC), and TJC + SJC in subjects with arthritis at baseline
 - o SDI (also change from baseline at the EOT visit, if prior to Week 24)
 - o EQ-5 D-5 L score
 - o PROMIS Fatigue 6 a
 - o Pain NRS

SLE 9.3.4 PK Endpoints

• Concentration values and PK parameters of branebrutinib and metabolites of clinical interest

SLE 9.4 Statistical Analyses

The SAP will be developed and finalized before database lock. Section SLE 9.4.1 provides a summary of planned statistical analyses of the primary and secondary endpoints. Additional and exploratory endpoints will be summarized in a descriptive manner.

SLE 9.4.1 Efficacy Analyses

Efficacy data will be summarized using the FAS. Data will be summarized using descriptive statistics (n, mean, standard deviation, median, minimum, and maximum), unless otherwise specified, for continuous variables, and frequency distributions (counts and percentages) for categorical variables. Efficacy data will be summarized separately for the SLE sub-protocol and with each sub-protocol combined for variables that are similar among the sub-protocols.

For the SLE sub-protocol, data will be presented for the following treatments:

- Branebrutinib
- PBO

Endpoint	Statistical Analysis Methods
Primary	General Analysis Methodology
	Response rates of branebrutinib compared to PBO for the primary endpoint will be analyzed using a Cochran-Mantel-Haenszel (CMH) test stratified by immunosuppressant use (yes/no). The 95% CI for each treatment group response rate and the difference in response rate for branebrutinib compared to PBO will be provided. If expected cell counts are not sufficient, then Fisher's exact test will be used. Since this sub-protocol is not powered to determine statistical significance, P-values will be added descriptively.
	Supportive Analyses
	Supportive analyses using logistic regression for the primary endpoint may be performed to incorporate additional covariates of interest and to confirm primary analysis results. The odds ratio and the corresponding 95% CI will be provided. Bayesian borrowing to utilize historical controls may also be performed as supportive analyses. Details will be provided in the SAP if needed.
	Imputation Method
	Nonresponder imputation will be used for binary endpoints for subjects who discontinue study treatment early, start a protocol-prohibited

Protocol Amendment No.: 04

Endpoint	Statistical Analysis Methods
	medication/therapy prior to the specified timepoint, or otherwise have missing endpoint data for the specified timepoint.
	Other imputation methods may be considered for sensitivity analyses and will be described in the SAP if used.
Secondary/	General Analysis Methodology
Additional	Response rates of branebrutinib compared to PBO for binary endpoints will be analyzed using a CMH test stratified by immunosuppressant use (yes/no). The 95% CI for each treatment group response rate and the difference in response rate for branebrutinib compared to PBO will be provided. If expected cell counts are not sufficient, then Fisher's exact test will be used.
	Continuous endpoints (change from baseline values) will be analyzed using analysis of covariance. The baseline value of the endpoint being tested will be added into the model as a covariate. Treatment differences based on least-squares means and corresponding 2-sided 95% CIs will be provided for the difference between branebrutinib and PBO.
	Supportive Analyses
	Supportive analyses using logistic regression for the primary endpoint may be performed to incorporate additional covariates of interest and to confirm primary analysis results. The odds ratio and the corresponding 95% CI will be provided.
	Supportive analyses for continuous endpoints may be performed using MMRM to investigate response over time.
	Imputation Method
	Nonresponder imputation will be used for binary endpoints for subjects who discontinue study treatment early, start a protocol-prohibited medication/therapy prior to the specified timepoint, or otherwise have missing endpoint data for the specified timepoint. Other imputation methods may be considered for sensitivity analyses and will be described in the SAP if used.
	Testing Strategy for Secondary Endpoints
	There will be no alpha level adjustment for multiple endpoint testing.

SLE 9.4.1.1 Subgroup Analyses

Subgroup analyses will be conducted for the primary and secondary efficacy endpoints on the FAS population. Subgroups that may be evaluated include the following:

• Gender

Clinical Protocol
BMS-986195
IM014029 - SLE
Branebrutinib

- Race
- Tobacco use

Additional subgroups defined for descriptive summaries may be specified in the SAP.

SLE 9.4.2 Safety Analyses

Safety data will be descriptive in nature and will be summarized using the Safety Analysis Set. Data will be summarized using descriptive statistics (n, mean, standard deviation, median, minimum, and maximum), unless otherwise specified, for continuous variables and frequency distributions (counts and percentages) for categorical variables. Safety data will be summarized separately for each sub-protocol and with all sub-protocols combined.

Data will be presented for the following treatments:

- Branebrutinib
- PBO

SLE 9.4.2.1 Adverse Events

TEAEs are defined as AEs that occur after the subject received first dose of study treatment or if a preexisting condition worsens in severity or becomes serious after receiving the first dose of study treatment up to 30 days after the last dose of study treatment. All reported TEAEs, SAEs, deaths, AEs leading to study treatment discontinuation, and AEIs will be summarized by Medical Dictionary for Regulatory Activities (MedDRA) system organ class and preferred term. AEIs in this study may include infections, influenza, tuberculosis, and herpes.

SLE 9.4.2.2 Clinical Laboratory Tests

Laboratory parameters will be summarized as absolute and change from baseline values by visit. Baseline values are defined as the last nonmissing value prior to the first dose of study treatment. Marked abnormalities summarized by visit and shift tables will also be provided. For clinical laboratory test results, marked abnormalities will be defined in the SAP.

SLE 9.4.2.3 Vital Signs and ECGs

Vital signs and ECGs will be summarized as absolute and change from baseline values by visit. Baseline values are defined as the last nonmissing value prior to the first dose of study treatment. Marked abnormalities will be summarized by visit as well. For vital signs and ECGs, marked abnormalities will be defined in the SAP.

SLE 9.4.3 Other Analyses

The PK, PD, and exploratory biomarker analyses will be described in the SAP finalized before database lock. Any population PK analysis and PD analyses will be presented separately from the main CSR.

SLE 9.4.4 Analysis and Reporting

After all subjects in the SLE sub-protocol have finished the study and the data have been locked for the sub-protocol, analyses of the efficacy and safety data for the sub-protocol will be performed in order to aid in planning for subsequent clinical development. Details of these analyses will be described in the SAP. The study team responsible for managing the study, including Medical Monitors, will remain blinded to treatment assignment and the results of safety analysis until full database lock and treatment unblinding has occurred. The data will be reported only after completion of all 3 sub-protocols.

Page: 112

Protocol Number: IM014029 IND Number: 142401

EX-US Non-IND

EUDRACT Number: 2019-002205-22

Date: 01-Jul-2019

Revised Date: 01-Dec-2021

Clinical Protocol IM014029:

PSS SUB-PROTOCOL

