- b) Any major surgery within the last 30 days before the first dose of study treatment, or any surgery planned during the course of the study.
- c) Cancer or history of cancer or lymphoproliferative disease (other than adequately treated cutaneous basal cell or squamous cell carcinoma with no evidence of recurrence within the previous 5 years), including pre-lymphoma (pseudolymphoma of the orbit and small intestine, lymphomatoid granulomatosis, angioimmunoblastic lymphadenopathy, and lymphoid interstitial pneumonitis).
- d) Class III or IV congestive heart failure as defined by the New York Heart Association (NYHA) or any recent onset of heart failure resulting in NYHA Class III/IV symptoms
- e) Acute coronary syndrome (eg, myocardial infarction, unstable angina pectoris) and/or any history of significant cerebrovascular disease within 24 weeks before the screening visit.
- f) Current or recent (within 3 months before randomization) gastrointestinal disease, including gastrointestinal surgery, that could impact the absorption of study treatment.
- g) **Not Applicable per Revised Protocol 03 -** Subjects with non-SLE concomitant illness that, in the opinion of the investigator, is likely to require additional systemic glucocorticosteroid therapy during the study (eg, asthma).
- h) Significant blood loss (> 500 mL) or blood transfusion within 4 weeks before randomization.
- i) Inability to tolerate oral medication.
- j) Inability to tolerate venipuncture and/or inadequate venous access.
- k) Recent (within 6 months before randomization) drug or alcohol abuse as defined by the Diagnostic Criteria for Drug and Alcohol Abuse in the Diagnostic and Statistical Manual of Mental Disorders 5 (DSM 5).
- 1) Any other sound medical, psychiatric, and/or social reason as determined by the investigator.
- m) Subjects with a diagnosis of antiphospholipid antibody syndrome.
- n) Any prior history of atrial fibrillation or flutter.
- o) Subjects with non-SLE concomitant illness that, in the opinion of the investigator, is likely to require additional systemic CS therapy during the study (eg, asthma).

2) Findings Related to Possible Infection: SLE Sub-protocol

- a) Not Applicable per Revised Protocol 03 Any of the following TB criteria:
 - History of active TB prior to screening visit, regardless of completion of adequate treatment.

- O Signs or symptoms of active TB (eg, fever, cough, night sweats, and weight loss) during screening as judged by the investigator.

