- g) Subjects with active, severe lupus nephritis (World Health Organization Class III or IV) that requires or may require treatment with cytotoxic agents or high-dose CS are excluded. Subjects with prior controlled renal disease with serum creatinine $\leq 2 \times$ ULN and either residual proteinuria ≤ 3 g/day or a UPCR of ≤ 3 mg/mg or 339 mg/mmol are allowed. Stability of renal disease must be documented with at least 2 measurements of proteinuria or UPCR over the past 6 months or with 2 tests during the screening period at least 1 week apart and must be approved by the Medical Monitor.

5) Prior/Concomitant Therapy: SLE Sub-protocol

- a) Inability to comply with restrictions and prohibited treatments as listed in Section SLE 6.7 Concomitant Therapy; inability to comply with discontinuation requirements (Section SLE 7.1).
- b) **Not applicable per Revised Protocol 03** Prior exposure to BTK inhibitors such as ibrutinib, acalabrutinib, or experimental drugs (eg, tirabrutinib, vecabrutinib, zanibrutinib, ARQ-531, GDC-0853, or others).
- c) Other investigational agents must be discontinued at least 12 weeks or 5 half-lives before the screening visit, whichever is longer.
- d) Exposure to JAK inhibitors such as tofacitinib, baricitinib, filgotinib, or upadacitinib within 8 weeks prior to randomization or during the study.
- e) Required discontinuation periods for immunomodulatory drugs (eg, cyclosporine, tacrolimus, etc) or biologic drugs (including those specifically listed below) are provided in SLE Table 6. If a drug is not specifically listed, consult the guidance. Usual discontinuation periods are 4 weeks or 5 half-lives, whichever is longer.
- f) Belimumab therapy within 6 months before randomization or during the study
- g) Subjects who have taken rituximab within 12 months prior to randomization; for subjects who received rituximab prior to this 12-month period, the B cell count should be within normal range. Rituximab is prohibited during the study.
- h) Abatacept therapy within 6 months prior to randomization or during the study.
- i) Therapy with other biologics such as tocilizumab and anakinra within 8 weeks prior to randomization or during the study.
- j) Cyclosporine or tacrolimus therapy within 8 weeks prior to randomization or during the study.
- k) Therapy with sulfasalazine, or similar drugs within 8 weeks prior to randomization or during the study.
- 1) IV immunoglobulin (IVIG) within 8 weeks prior to randomization or during the study.

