	Topical and inhaled CS	allowed if lesions/rash resolve	Not applicable
		completely. Inhaled CS for	
		nonlupus conditions will not	
		count against the maximum CS	
		dose	
		Must have been taken for ≥ 12	
		weeks before the screening visit	
		and must be at a stable dose for	10 1 10
A	Chl	\geq 8 weeks before the screening	12 weeks if not
Antimalarial drugs	Chloroquine and quinacrine	visit and remain stable until randomization and throughout	continuing as background SOC
		study participation. New	background SOC
		initiation or change in dose	
		during treatment is not permitted	
		Doses of > 400 mg/day are not	
		permitted	12 weeks if not
	Hydroxychloroquine (HCQ)	New initiation or dose increase	continuing as
		during treatment is not	background SOC
		permitted. Whole blood levels at	G 2 2 3
		screening must be $\leq 2 \mu g/mL$ Treatment with anticoagulant or	
		antiplatelet therapies, including	
Anticoagulant or	Anticoagulant or antiplatelet	aspirin for cardioprotection,	
Antiplatelet therapies	therapies, including aspirin	within 2 weeks prior to	2 weeks
	for cardioprotection	randomization or during the	
		study	

Protocol Amendment No.: 04

Date: 01-Dec-2021 78

SLE Table 6 Prohibited and Restricted Medications

Type of Medication	Examples of Medications	Restrictions	Required Washout Period Prior to and Postrandomization
Anti-TNF therapy	Adalimumab, certolizumab, etanercept, golimumab, infliximab, and TNF biosimilars	Prohibited during the study	3 months
Biologics	Rituximab	Prohibited during the study	12 months
	Belimumab	Prohibited during the study	6 months
	Abatacept	Prohibited during the study	6 months
	Other Biologics, including tocilizumab, anakinra		8 weeks
	IVIG	Prohibited during the study	8 weeks
Immunosuppressants (allowed) Note: combinations of immunosuppressants are not allowed	Azathioprine, 6-MP, MTX, leflunomide, MMF	Must have been taken for ≥ 12 weeks before the screening visit and must be at a stable dose for ≥ 8 weeks before the screening visit and remain stable until randomization and throughout study participation. New initiation or dose changes during treatment are not permitted.	12 weeks if not continuing as background SOC, except leflunomide 36 weeks before screening
Immunosuppressants (prohibited)	Cyclosporine, tacrolimus, thalidomide and similar (oral); topical calcineurin inhibitors (tacrolimus, pimecrolimus)	Prohibited during the study	8 weeks
O.I. D.M.D.	Cyclophosphamide	Prohibited during the study	24 weeks

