- p) Subjects who have a history of full-thickness corneal transplantation (penetrating keratoplasty); however, subjects who have had endothelial keratoplasty are not excluded.
- q) Subjects who have had cataract surgery within 6 months prior to randomization
- r) Subjects are not permitted to have new installation of lacrimal punctum plugs within 4 weeks of randomization. Subjects with existing lacrimal punctum plugs are permitted to enroll, and have these plugs replaced as necessary during the study.
- s) For oral CS restrictions, see Section pSS 6.7.1.
- t) Other CS: IM, IV, IA, or oral modified-release CS treatment within 4 weeks before randomization or during the study
- Not Applicable per Revised Protocol 03 Treatment with DMARDs (excluding HCQ) or immunomodulators within 4 weeks before randomization; MTX treatment within 12 weeks before randomization or during the study. HCQ whole blood concentration >2 μg/mL (at screening only) is exclusionary. HCQ dose > 400 mg/day, new initiation, or dose increases during treatment are not permitted.
- v) Antimalarial treatment (HCQ is permitted, but must be stable; initiation or change in dose during treatment is not permitted. Quinacrine or chloroquine treatment is not permitted during the study or within 4 weeks before randomization. For HCQ, see above criterion for requirements.

- w) Current or past approved or investigational biologic DMARD treatments (eg, IL-6 inhibitors, IL-1 inhibitors, T cell modulators, and anti-CD20 agents [eg, rituximab]), other than abatacept treatment, within 12 months before randomization or during the study
- x) Anti-TNF therapy such as adalimumab, certolizumab, etanercept, golimumab, infliximab, or biosimilars within 3 months before randomization or during the study
- y) **Not applicable per Revised Protocol 03 -** Administration of a live vaccine within 90 days or an inactivated vaccine within 30 days before randomization; furthermore, live or inactivated vaccines should not be used during treatment or within the 14 days following the final dose of study treatment
- z) Treatment with tricyclic antidepressants (eg, amitriptyline, desipramine, doxepin, imipramine, nortriptyline, trimipramine) or quetiapine, within 4 weeks before randomization
- aa) Treatment with anticoagulant or antiplatelet therapies, including aspirin for cardioprotection, within 2 weeks prior to randomization or during the study

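### In SLE, the 12-month washout and the B cell condition apply to rituximab by name only, so another approved anti-CD20 biologic needs as little as 8 weeks

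*Combined protocol and SAP*

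**What the plan says.** **SLE 5.2, item 5 (Prior/Concomitant Therapy).**

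- 5g excludes "Subjects who have taken rituximab within 12 months prior to randomization" and adds that "for subjects who received rituximab prior to this 12-month period, the B cell count should be within normal range". It names rituximab only.
- 5i is the catch-all: "Therapy with other biologics such as tocilizumab and anakinra within 8 weeks prior to randomization or during the study".
- 5e sends the reader to SLE Table 6 for required periods and then says: "If a drug is not specifically listed, consult the guidance. Usual discontinuation periods are 4 weeks or 5 half-lives, whichever is longer".
- 5c deals separately with unapproved products: "Other investigational agents must be discontinued at least 12 weeks or 5 half-lives before the screening visit, whichever is longer".

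**SLE 6.7.1, SLE Table 6.** The biologics rows give rituximab 12 months, belimumab 6 months and abatacept 6 months. The row "Other Biologics, including tocilizumab, anakinra" has 8 weeks. No row names the anti-CD20 class, and none carries a B cell condition.

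**pSS 5.2, item 5.** 5w works by class. Its list of biologic DMARDs ends "T cell modulators, and anti-CD20 agents [eg, rituximab]), other than abatacept treatment, within 12 months before randomization or during the study".

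**pSS 6.7.1, pSS Table 6.** This has the same layout as the SLE table: rituximab by name at 12 months, other biologics (tocilizumab, anakinra) at 8 weeks.

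**The concern.** The condition in 5g shows what the sponsor wants to guard against: B cells that have not recovered, even after the drug itself has cleared. That reasoning applies to any approved anti-CD20 depleting agent, but the text attaches it to one product. Neighbouring SLE criteria are written by class with examples (JAK inhibitors in 5d, anti-TNF therapy in 5r, BTK inhibitors in 5u), so the single name in 5g looks like a drafting gap.

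What is at stake is the safety of an individual subject. Someone with residual depletion could meet the written washout rules and be randomized. SLE 8.2.1 treats infections as potential events of interest, and SLE 2.2 reports decreases in B cells among the nonclinical findings. Against that, Master Protocol 1.1 expects BTK inhibition to act without depleting B cells. Such a subject's on-study B cell measurements would also be harder to interpret.

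**Working it through.** The plan gives no figure of its own to reproduce. The check is a comparison of rules followed by simple arithmetic.

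**Step 1: which SLE rules reach an approved anti-CD20 biologic other than rituximab?**

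- 5g and the Table 6 rituximab row do not, because they name rituximab.
- 5c does not, because the drug is not investigational.
- 5i and the Table 6 row for other biologics do: 8 weeks.
- 5e also does, since the drug is not listed by name: consult the guidance, with a usual period of 4 weeks or 5 half-lives.
- 5y only refers back to the required washout.

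**Step 2: how do 5i and 5e combine?** SLE 5.2 opens by excluding anyone who meets any one of its criteria. The criteria are cumulative, so 8 weeks under 5i is a floor whatever 5e says, and 5e can only lengthen it. Leaving aside discretion under the guidance, the required washout is max(8 weeks, 5 × half-life). The 4-week limb never governs for this group.

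**Step 3: gap against 12 months.** 12 months = 365/7 = 52.1 weeks. The documents give no half-life for any such drug; the values below are assumptions chosen to show the range.

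| Assumed half-life | 5 half-lives | Required washout | Shortfall against 52.1 weeks |
|---|---|---|---|
| 1 week | 5 weeks | 8 weeks | 44.1 weeks |
| 2 weeks | 10 weeks | 10 weeks | 42.1 weeks |
| 3 weeks | 15 weeks | 15 weeks | 37.1 weeks |
| 4 weeks | 20 weeks | 20 weeks | 32.1 weeks |

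Break-even points: 5 half-lives exceeds 8 weeks (56 days) only above 56/5 = 11.2 days, and reaches 12 months only at 365/5 = 73 days.

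**Step 4: the pSS comparison.** pSS 5w applies 12 months to the class. pSS is not a clean standard, though. pSS Table 6 names only rituximab, pSS has no B cell condition, and 5w puts IL-6 and IL-1 inhibitors at 12 months while pSS 5e gives tocilizumab and anakinra 8 weeks. 5w is used here only for the anti-CD20 period. The SLE gap follows from 5g against 5i without it.

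**Step 5: who could be affected?** SLE exclusion 1c removes "Cancer or history of cancer or lymphoproliferative disease", apart from certain treated skin cancers. Exclusion 4e removes other immune-mediated diseases, including multiple sclerosis. What remains is mainly earlier use for SLE itself or for a permitted comorbidity such as secondary Sjögren's syndrome. Master Protocol 1.2.1.1 makes such use plausible, since it mentions other B-cell-targeting approaches in lupus and off-label agents, but it identifies no depleting product and gives no frequency.

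**The case against.** The strongest reply is that review would catch the case. Prior SLE medications since diagnosis are recorded (SLE 6.7.1). Eligibility is confirmed before randomization by the Medical Monitor or the central lupus review (SLE 5). 5e tells the site to consult guidance for unlisted drugs. Exclusions 1a, 1l and 6c allow exclusion on judgment. These are real safeguards and could lead to a longer washout. None of them sets a period or a B cell threshold for such a drug, so a reviewer applying 5i literally could accept the subject at 8 weeks.

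A second reply is that pSS is inconsistent too and that the affected group is not documented. Both parts stand, and they limit how much weight the point can carry.

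Three stronger readings are tempting and are not supported:

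- A reader might infer from 5e that 4 weeks could suffice. It could not, because 5i applies as well.
- A reader might infer that no B cell count is taken before randomization. Screening biomarker rows are blank in the public copy, so that cannot be concluded. SLE Table 2 schedules lymphocyte subsets (TBNK) at Week 0, so depletion would show at baseline, although a Day 1 result may arrive after randomization. What is missing is a rule, not demonstrably a test.
- A reader might infer biased efficacy results. The rule operates before randomization and applies equally to both arms.

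**Conclusion.** The point holds as a minor safety matter. For an approved anti-CD20 biologic other than rituximab, the SLE text sets a firm floor of 8 weeks, extended by 5e where five half-lives or the guidance asks for more, and no B cell condition. That is weaker than the sponsor's rule for rituximab in SLE and weaker than the washout for the class in pSS 5w. The shortfall is at most about 44 weeks, and about 32 to 44 weeks under the assumed half-lives.

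The number of subjects is unknown and probably very small. Between-arm bias, sample size, power and the definition of the mCLASI/steroid primary endpoint are unaffected. The documents do not show that any exposed subject would in fact be enrolled or harmed, so this should not be presented as a demonstrated hazard. Investigational agents are outside the point, and the RA sub-protocol body is not in the available text and is not covered.

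**What to change.** Reword SLE 5g and the SLE Table 6 rituximab row to cover *rituximab or other anti-CD20 B-cell-depleting agents*: 12 months, with a B cell count within normal range for earlier exposure. Align the pSS Table 6 rituximab row with pSS 5w so that table and criterion name the same class. A sentence in SLE 5e or 5i stating that the longer of 8 weeks and 5 half-lives applies to any other unnamed biologic would help sites, but it is optional because the cumulative criteria already imply the 8-week floor.

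The cost is a few words in one criterion and two table rows. No new medication history is needed, since prior SLE treatments are already recorded. The only downside is possibly a very small loss of eligible subjects.
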